12.3.5. Safety variables

Adverse Events and Neonatal Morbidities

- Number and percent of neonates reporting AEs started during procedure for surfactant administration as well as AEs started during the procedure and judged related to the procedure will be summarized by treatment group.

For LISA group, any AE assessed as related to CHF 6440 catheter will be considered procedure-related.

These events will be also summarized by treatment group based on action required, if any (i.e. supplementary oxygen or transient increase in FiO₂, manual positive pressure ventilation, endotracheal intubation, administration of, crystalloids, or cardiopulmonary resuscitation or administration of adrenaline). The duration of endotracheal intubation and positive pressure ventilation will be

summarized as well.

A subgroup analysis of AEs during procedure for surfactant administration will be performed based on the use of sedation and/or analgesia (Yes/No).

- Incidence of AEs including neonatal complications of prematurity (see [APPENDIX III](#) for complete list), related AEs (ADRs), serious AEs (SAEs) and AEs leading to death will be summarized by treatment group both in term of frequency of neonates with at least one AE and in term of frequency of AEs (number of events). All the aforementioned categories of AEs will be summarized by System organ Class (SOC) and Preferred Term (PT).
- Frequency of neonates with major neonatal morbidities at discharge or 40 weeks PMA (whichever comes first) will be summarized by treatment group.

Vital Sign

- Vital signs parameters (SBP, DBP MBP, HR and RR) will be summarized as absolute and the change from baseline (pre-procedure) by treatment group using descriptive statistics.

Pain assessment

- PIPP score will be summarized by treatment group by means of descriptive statistics.

First administration

- Number of 1st failed attempt to insert the catheter/ETT will be summarized by treatment group. Percentage of neonates with 1st failed attempt will be compared between group using the Cochran-Mantel-Haenszel adjusted for gestational age group. The CMH adjusted difference with its 95% CI will be presented.
- Number of attempts to the first successful insertion will be summarized by treatment group by means of descriptive statistics.
- Number of device misallocation (i.e., esophageal intubation) will be summarized by treatment group by means of descriptive statistics.
- Number of maneuvers discontinued due to neonate's severe destabilization will be summarized by treatment group by means of descriptive statistics.
- Duration of surfactant administration (min) and overall procedure for surfactant administration will be compared between treatment groups by using the Mann-Whitney U- test.

Mortality and BPD

- Death/BPD incidence at 36 weeks PMA will be compared by treatment by means of CMH test, adjusting for GA group and related 95% confidence interval will be provided.

- The incidence of BPD at 36 weeks PMA will be compared by treatment as for Death/BPD incidence.
- The mortality at 36 weeks PMA and at Day 28 will be compared by treatment as for Death/BPD incidence.
- Oxygen use at Day 28 (alone and / or during any kind of MV) will be compared by treatment as for Death/BPD incidence.

Other safety variables

- Feeding and hearing status at discharge or 40 weeks PMA (whichever comes first) will be summarized by treatment group by frequency distributions.
- Weight, OFC and length at discharge home or 40 weeks PMA will be summarized by treatment group by descriptive statistics.
- Neonates needing invasive or non-invasive respiratory support at discharge home or 40 weeks PMA will be summarized by treatment group by frequency distribution
- Neonates needing respiratory medications at discharge home or 40 weeks PMA will be summarized by treatment group by frequency distribution

Health status questionnaire at 24 months (± 3 months) corrected age

(This stand-alone assessment will be analyzed and reported separately from the main phase)

- Bayley Scales of Infant Development (cognitive and language scores) will be summarized using descriptive statistics by treatment group and BSID version (III or IV).
- Vital signs and all other variables collected through the questionnaire (i.e., anthropometric measures, cerebral palsy, seizures, feeding method, functional disability and respiratory morbidity) will be summarized by treatment group by frequency distribution or descriptive statistics, as appropriate.

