2. STUDY OBJECTIVES

2.1 Primary Objective(s)

The main objective of this study is to evaluate the safety profile of the administration of porcine surfactant (poractant alfa, Curosurf®) through a less invasive method (LISA) using a thin catheter (CHF 6440) during non-invasive ventilation (NIV) (CPAP, NIPPV, BiPAP), compared to an approved conventional surfactant administration during invasive ventilation and rapid extubation, in spontaneously breathing preterm neonates with clinical signs of respiratory distress syndrome (RDS). The short-term and mid-term safety will be assessed: adverse events and adverse drug reactions occurring during overall procedure for surfactant administration, neonatal pain assessment pre- and during surfactant administration, duration of surfactant administration, incidence of BPD at 36 weeks post menstrual age (PMA), major neonatal morbidities and vital signs.

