12. STATISTICAL METHODS

12.1. Sample Size

No primary efficacy endpoint was defined in this study since the main objective is to describe the overall safety and efficacy profile of administering poractant alfa with two different

procedures: LISA technique or conventional administration with endotracheal tubes and brief invasive ventilation. A total of 150 neonates will be randomized in the study with a ratio 2:1 to LISA arm (i.e. 100) and conventional administration arm (i.e. 50).

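### Procedural AEs, procedure-related AEs, major morbidities and PIPP fall within the comparative main objective but have no planned between-arm difference or confidence interval

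*Protocol*

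**What the plan says.** Protocol section 2.1 states the main objective as the safety profile of LISA "compared to an approved conventional surfactant administration during invasive ventilation and rapid extubation". The components it lists begin with "adverse events and adverse drug reactions occurring during overall procedure for surfactant administration", followed by pain assessment, and then "duration of surfactant administration, incidence of BPD at 36 weeks post menstrual age (PMA), major neonatal morbidities and vital signs".

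Section 12.3.5 fixes the analysis of these components:

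- Neonates with any AE starting during the procedure, and those with "AEs started during the procedure and judged related to the procedure will be summarized by treatment group".
- "Frequency of neonates with major neonatal morbidities at discharge or 40 weeks PMA (whichever comes first) will be summarized by treatment group".
- "PIPP score will be summarized by treatment group by means of descriptive statistics".

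The Statistical methods part of the Protocol Outline says the same. In the same section, failed first insertion attempt is compared by CMH adjusted for GA group, and "The CMH adjusted difference with its 95% CI will be presented". Death/BPD, BPD, mortality and oxygen use at Day 28 are also compared by CMH adjusted for GA group, with a 95% CI.

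Section 12.3.1 limits categorical variables to number and percent. Numeric variables also get a 95% CI as a descriptive statistic within each arm. Section 12.1 describes the aim in softer terms: "No primary efficacy endpoint was defined in this study since the main objective is to describe the overall safety and efficacy profile".

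**The concern.** A comparative objective is answered by a contrast between arms with its uncertainty. For procedural AEs and pain, the components named first in section 2.1, the plan gives two sets of by-arm figures and leaves the contrast to the reader. In an unequal 100 versus 50 split, a gap between two percentages can easily be taken as a difference, and a small gap as equivalence, when the data support neither.

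The gap matters more because of what the protocol expects. Section 1.2 reports that desaturation, apnea, bradycardia, coughing, choking and surfactant reflux have been seen more often during LISA. It also cites more focal intestinal perforation in neonates below 26 weeks (10% versus 7.4%). The hoped-for benefits, less mechanical ventilation and less death or BPD, get adjusted comparisons with intervals. The anticipated procedural harms, and focal intestinal perforation (listed in Appendix III), do not.

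**Working it through.** **Step 1. Set the components of section 2.1 beside their planned analysis in section 12.3.5.**

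| Component named in 2.1 | Planned analysis | Between-arm interval? |
|---|---|---|
| Procedural AEs, including procedure-related | Number and percent by arm | No |
| Pain (PIPP) | Descriptive statistics by arm | No (within-arm CI only, 12.3.1) |
| Duration of administration | Mann-Whitney test | Test only; no estimate or CI named |
| BPD at 36 weeks PMA | CMH adjusted for GA group | Yes, 95% CI |
| Major neonatal morbidities | Frequency by arm | No |
| Vital signs | Descriptive statistics by arm, with change from baseline | No (not pursued here) |

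Compared by CMH with a 95% CI although not named in 2.1: failed first attempt, Death/BPD, mortality and oxygen use at Day 28. The protocol therefore chooses variable by variable between summarising and comparing.

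**Step 2. Check the sample size.** Section 12.1 gives 150 neonates at 2:1. 150 × 2/3 = 100 and 150 × 1/3 = 50, so the split agrees. No alpha, power, event rate or precision target is given, so the total of 150 cannot be reproduced.

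**Step 3. Size of the missing interval for a proportion.** The event rates are assumed, equal in both arms. The simple Wald interval stands in for the GA-stratified one:

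half-width = 1.96 × √[p(1−p)(1/100 + 1/50)]

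| Assumed rate p | Half-width (percentage points) |
|---|---|
| 5% | 7.4 |
| 10% | 10.2 |
| 20% | 13.6 |
| 30% | 15.6 |
| 40% | 16.6 |
| 50% | 17.0 |

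For example, at p = 0.10: 1.96 × √(0.09 × 0.03) = 1.96 × 0.0520 = 0.102.

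An invented illustration with unequal rates, 35% of 100 versus 20% of 50: 0.15 ± 1.96 × √(0.35 × 0.65/100 + 0.20 × 0.80/50) = 0.15 ± 0.145, or about +0.5 to +29.5 points. The two percentages alone do not show that range.

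**Step 4. Size of the missing interval for PIPP.** Half-width = 1.96 × SD × √(1/100 + 1/50) = 0.34 SD. For an assumed SD of 2 to 5 points this is 0.7 to 1.7 points.

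**Step 5. Sparse morbidities.** With no events in an arm, the estimated variance for that arm is zero and the Wald formula fails. The exact one-sided 95% upper limit is still 1 − 0.05^(1/100) = 3.0% for 0/100 and 1 − 0.05^(1/50) = 5.8% for 0/50. Rare morbidities therefore need a method suited to small counts.

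**Step 6. Observation window.** Under section 10.8 the procedure starts with the laryngoscope in both arms. It ends when the catheter is removed in the LISA arm and when the ETT is removed in the control arm, within one hour of instillation. The time at risk for a procedural AE can therefore be much longer in controls.

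**The case against.** The strongest reply is that the trial is descriptive by declaration. Section 12.1 says so, section 1.1 calls the study explorative, and by-arm counts are a normal way to report AEs. This rules out confirmatory claims. It does not argue against a difference with an interval, which is itself description. Nor was descriptive intent the rule that divided the variables, since the same section compares many others.

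A second reply is that section 12.3 defers detail to a separate SAP, which could add the columns. It could, and nothing in the wording forbids it. But the protocol has already said which variables are compared and which are only summarised, so a SAP that follows it would leave these four without a contrast.

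A third reply is that the remedy has weaknesses. The unequal AE window means that an interval on procedural AEs could lend precision to a contrast with unequal exposure time. Appendix III has ten headings, some likely to be sparse with 50 controls, so intervals for every morbidity would be many and unadjusted for multiplicity. Both points stand and shape the fix.

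A reader might infer that the trial offers no between-arm estimate or interval at all for its main question, or that its inferential effort sits on the wrong variables. The protocol does not support either. BPD, a named component of section 2.1, is compared with a 95% CI, duration of administration is tested, and Death/BPD and mortality are important safety outcomes that are also compared. PIPP will at least show uncertainty within each arm.

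**Conclusion.** The point holds for four sets of variables: any procedural AE, procedure-related AEs, major morbidities and PIPP. They belong to a comparative main objective and are planned as by-arm summaries only, while other safety variables in the same section get a GA-adjusted comparison with a CI. This is a stated analysis choice that fits the objective poorly. It does not invalidate the design, and the trial's main safety question is not left wholly without a contrast.

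The omitted intervals would be wide: about ±10 to ±17 points for event rates of 10% to 50%, and about 0.34 SD for PIPP. These sizes rest on assumed rates and SDs, full recruitment of 100 and 50, and an unstratified approximation. The gap does not depend on those assumptions. It is worth correcting because the remedy is cheap and uses a method already in the plan.

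**What to change.** In section 12.3.5 and the matching part of the Protocol Outline:

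- Add the GA-stratified risk difference with 95% CI for the percentage of neonates with (a) any AE starting during the procedure and (b) any procedure-related AE. The GA groups are already randomisation strata (section 6.5).
- Add a GA-adjusted mean or median difference with 95% CI for PIPP.
- Do the same as (a) and (b) for major neonatal morbidities, naming an interval method suited to sparse strata where events are few.
- State that all of these are estimates, without hypothesis testing or a confirmatory claim.
- Report procedure duration by arm beside (a) and (b), and note that the AE window ends at a different event in each arm.

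The cost is protocol and SAP wording plus a few table columns. No extra neonates, visits or data are needed. The small downside is a larger set of wide intervals that are not adjusted for multiplicity.

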Sample size calculation	
No primary efficacy endpoint was defined in this study since the main objective is to describe the overall safety and efficacy profile of administering poractant alfa with two different procedures: LISA technique or conventional administration with endotracheal tube and brief invasive ventilation. A total number of one hundred-fifty (150) neonates is deemed appropriate for the study aim. Neonates will be randomized with a ratio 2:1 to the LISA technique arm (i.e. 100 neonates) and to the conventional technique (i.e. 50 neonates).

Statistical methods	
Safety variables
 
 Number and percent of neonates reporting AEs started during procedure for surfactant administration as well as AEs started during the procedure and judged related to the procedure will be summarized by treatment group. 
For LISA group, any AE assessed as related to CHF 6440 medical device will be considered procedure-related.
 
These events will be also summarized by treatment group based on action required, if any (i.e. supplementary oxygen or transient increase in FiO₂, manual positive pressure ventilation, endotracheal intubation, administration of crystalloids, cardiac massage or administration of adrenaline). The duration of endotracheal intubation (invasive ventilation) and manual positive pressure ventilation will be summarized as well.
 
A subgroup analysis of surfactant- and procedure- related AEs will be performed based on the use of sedation and/or analgesia (Yes/No).
 
 Incidence of all the AEs (including neonatal complications of prematurity), related AEs (ADRs), serious AEs (SAEs) and AEs leading to death will be summarized by treatment group both in terms of frequency of neonates with at least one AE and in terms of frequency of AEs (number of events). All the aforementioned

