5.1 Permitted concomitant Medications

Any concomitant medication required for the normal care of preterm neonates will be permitted during the study and recorded in the eCRF.

The use of sedative/analgesic medication, as well as the use of atropine, before / during surfactant administration, will be at investigator’s discretion and according to each neonatal intensive care unit (NICU) internal standard practice. If premedication is used, the Investigator should define a protocol (with specification of drugs and dosages) before starting enrollment, which allows for a step-by-step management of pain and sedation for the endotracheal administration of surfactant. Each neonate will be managed according to the pre-defined protocol, and decision on which step of the protocol to apply should be based on neonate’s needs. The same step-by-step protocol should be applied to both treatment arms. The protocol will be provided to the Sponsor.

If caffeine is administered, it should be used in both treatment arms.

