6.2.3.2 Sedation and analgesia

The use of sedative/analgesic medication, as well as the use of atropine, before/during surfactant administration, will be at investigator's discretion and according to each neonatal intensive care unit (NICU) internal standard.

If premedication is used, the Investigator should define a protocol (with specification of drugs and dosages) before starting enrollment, which allows for a step-by-step management of pain and sedation for the endotracheal administration of surfactant. Each neonate will be managed according to the pre-defined protocol, and decision on which step of the protocol to apply should be based on neonate's needs. The same step-by-step protocol should be applied to both treatment arms. The protocol will be provided to the Sponsor.

A first step could be attempted with a non-pharmacological analgesic technique (sucrose, glucose, holding, swaddling and methods of sensorial saturation).

A pharmacological intervention could be given following a progression in the use of sedatives/analgesics, based on neonate's need. As a guidance, examples of pharmacological interventions which can be used (either alone or in combination) are the following:

- Vagolytic agents (e.g. atropine).
- Sedative/analgesics medications with rapid onset and short duration of action (e.g. fentanyl).

The use of sedation/analgesia and other medications will be carefully recorded along with related information (e.g. date and time of administration, dosage and route) in the relevant section of the eCRF.

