12.3.4. Efficacy variables

Need for mechanical ventilation/intubation

- Percentage of neonates needing invasive mechanical ventilation in the first 72 hours of life, in the first 28 days PNA and within 36 weeks PMA will be compared between group using the Cochran-Mantel-Haenszel (CMH) test adjusted for gestational age group. The CMH adjusted difference with its 95% CI will be presented. Additional analysis will be performed to explore the impact of use of sedation and/or analgesia.
- Percentage of neonates needing any intubation procedure, outside the initial surfactant administration period, in the first 72 hours of life, 28 days PNA and within 36 weeks PMA will be compared between treatments as need for IMV.

SpO₂

- SpO₂ will be analyzed using a linear mixed model for repeated measures (MMRM) including treatment, time point, treatment by time point interaction, and gestational age group as fixed effects and pre-procedure SpO₂ as covariate. The adjusted means in each treatment group, the adjusted mean difference between treatments and their 95% CIs at each time point and averaged over the first 120 hours post-treatment will be estimated by the model. Time profile plot of mean SpO₂ in the first 120 hours post-administration will be presented by treatment group.
- SpO₂ will be summarized by treatments on neonates still receiving respiratory support at 28±2 PNA and 36 weeks PMA by means of descriptive statistics.

FiO₂

- FiO₂ will be analyzed using a linear MMRM including treatment, time point, treatment by time point interaction, and gestational age group as fixed effects and pre-procedure FiO₂ as covariate. The adjusted means in each treatment group, the adjusted mean difference between treatments and their 95% confidence intervals (CIs) at each time point and averaged over the first 120 hours post-treatment will be estimated by the model. Time profile plot of mean FiO₂ in the 120 hours post-treatment will be presented by treatment group.
- FiO₂ will be summarized by treatments on neonates still receiving respiratory support at 28±2 PNA and 36 weeks PMA by means of descriptive statistics.

SpO₂/FiO₂ ratio

- SpO₂/FiO₂ will be analyzed using a linear MMRM including treatment, time point, treatment by time point interaction, and gestational age group as fixed

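### The sedation/analgesia subgroup for procedural adverse events is split on actual use after open-label allocation, so its LISA v ETT contrasts are not randomised comparisons; the synopsis and section 12.3.5 also name different event sets

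*Protocol*

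**What the plan says.** **The split.** Protocol section 12.3.5 plans a subgroup analysis of all AEs during the surfactant procedure, to be "performed based on the use of sedation and/or analgesia (Yes/No"). The Protocol outline, under Statistical methods, describes what should be the same analysis with a different event set: "A subgroup analysis of surfactant- and procedure- related AEs will be performed based on the use of sedation and/or analgesia (Yes/No").

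**Who decides, when and on what grounds.** Under section 6.2.3.2, sedatives and analgesics "before/during surfactant administration, will be at investigator's discretion". Section 5.1 says the "decision on which step of the protocol to apply should be based on" the neonate's needs, and 6.2.3.2 adds: "A pharmacological intervention could be given following a progression in the use of sedatives/analgesics, based on" need. Section 7.1.2 places randomisation before the procedure, and section 3 describes the study as open-label. Section 6.5 stratifies by site and gestational age group only.

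**The safeguard.** Section 6.2.3.2 also says: "The same step-by-step protocol should be applied to both treatment arms". Where premedication is used, the site is to write that protocol before enrolment starts and give it to the sponsor. Date and time of each sedative or analgesic are recorded.

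**A related analysis.** For need for invasive mechanical ventilation (MV), section 12.3.4 says only: "Additional analysis will be performed to explore the impact of use of sedation and/or analgesia".

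**The concern.** A subgroup keeps the protection of randomisation only if membership is fixed before allocation or cannot be influenced by it. Neither holds here. The clinician knows the arm, knows whether a thin catheter or an endotracheal tube is about to be passed, and moves up the sedation steps as the neonate seems to need it. If one arm is sedated at a lower threshold of need, the sedated neonates in that arm are on average less sick, and so are its unsedated neonates. Both subgroup contrasts then shift in the same direction, which a reader could take for a consistent finding.

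The order of events adds a second problem. Because use during administration counts, a sedative given in response to bradycardia or desaturation moves that neonate into the Yes group because of the outcome.

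Procedural AEs are the first group of safety variables in section 9, and safety is the main objective, so these tables will be read. The two descriptions of the event set would also produce two different tables.

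**Working it through.** **Plan's own figures.** The Protocol gives no sedation rate, AE rate or power calculation. The only figure to reproduce is the 2:1 allocation in section 12.1: 150 × 2/3 = 100 LISA and 150 × 1/3 = 50 ETT. It reproduces.

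**Method.** Assume that neither arm nor sedation affects AE risk, and that need has the same distribution in both arms by randomisation. For arm *a*, the expected AE rate among the sedated is

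Σ share × P(use | need, *a*) × risk(need) ÷ Σ share × P(use | need, *a*),

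and among the unsedated the same with 1 − P(use | need, *a*). All rates below are assumptions.

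**Model 1: need in equal thirds, AE risk 20/40/60%, overall 40% in both arms.**

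Hard thresholds: LISA sedates only the highest third, ETT the upper two thirds.
- Sedated: LISA 60%; ETT (40 + 60)/2 = 50%; difference +10.
- Not sedated: LISA (20 + 40)/2 = 30%; ETT 20%; difference +10.

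Soft thresholds: use by need 10/20/60% in LISA and 50/70/90% in ETT (30% v 70% overall).
- Sedated: LISA (0.02 + 0.08 + 0.36)/0.9 = 51.1%; ETT (0.10 + 0.28 + 0.54)/2.1 = 43.8%; difference +7.3.
- Not sedated: LISA 0.74/2.1 = 35.2%; ETT 0.28/0.9 = 31.1%; difference +4.1.

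| Variant | Use LISA v ETT | Sedated, LISA − ETT | Not sedated, LISA − ETT |
|---|---|---|---|
| Hard thresholds | 33% v 67% | +10 | +10 |
| Soft thresholds | 30% v 70% | +7.3 | +4.1 |
| Soft, risk 30/40/50% | 30% v 70% | +3.7 | +2.1 |
| Closer use | 45% v 60% | +1.9 | +2.3 |
| Hard, LISA sedated more | 67% v 33% | −10 | −10 |
| Equal, need-driven use | 60% v 60% | 0 | 0 |
| Unequal use, unrelated to need | 30% v 70% | 0 | 0 |

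**Model 2: continuous severity.** AE log-odds rise by 1 per SD of severity, with the intercept (−1.19) set for 27% overall in both arms. A neonate is sedated when a normal need score, correlated ρ with severity, exceeds an arm-specific threshold. Differences are taken before rounding.

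| Use LISA v ETT | ρ | Sedated LISA v ETT | Difference | Not sedated LISA v ETT | Difference |
|---|---|---|---|---|---|
| 30% v 80% | 0.7 | 41.6% v 30.7% | +11.0 | 20.7% v 12.4% | +8.3 |
| 40% v 70% | 0.7 | 38.8% v 32.5% | +6.4 | 19.1% v 14.3% | +4.8 |
| 30% v 80% | 0.3 | 33.0% v 28.7% | +4.3 | 24.4% v 20.3% | +4.1 |
| 50% v 60% | 0.7 | 36.5% v 34.4% | +2.1 | 17.5% v 16.0% | +1.6 |
| 50% v 60% | 0.3 | 31.0% v 30.2% | +0.8 | 23.0% v 22.2% | +0.8 |

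In the first row the arms still agree overall: LISA 0.30 × 41.6 + 0.70 × 20.7 ≈ 27%; ETT 0.80 × 30.7 + 0.20 × 12.4 ≈ 27%. The artefact comes from the split alone.

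**Precision at the trial's size.** Half-width = 1.96 × √[p(1 − p)(1/n₁ + 1/n₂)].
- Model 1, hard thresholds, p = 0.40: sedated 33 v 33 gives 24 points; not sedated 67 v 17 gives 26.
- Model 2, first row, p = 0.27: sedated 30 v 40 gives 21 points; not sedated 70 v 10 gives 29.

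**With a pre-randomisation classifier.** If class membership does not depend on arm, the weights in the formula are the same for both arms and the expected false difference is 0.

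**The case against.** - **No text shows that use will differ by arm.** A reader might infer that sedation depends on the arm, so that the tables are bound to show a spurious LISA effect. The Protocol does not support that. It gives no sedation rates, and its one statement about the arms asks for the same step-by-step protocol in both. This stands as a limit on the claim. It does not remove the concern, because a common protocol fixes the available steps and not the step each neonate reaches.
- **The larger figures need strong inputs.** True. The 8 to 11 points of the continuous model need 30% v 80% use and a correlation of 0.7; milder inputs give about 1 to 4 points. All of these are below the precision of the subgroups.
- **The consequence is limited.** The study is exploratory, section 12.3.5 names no test within the subgroup, and the all-neonate AE summary is untouched. This stands.
- **The MV analysis.** A reader might infer that 12.3.4 plans the same Yes/No split for MV. It does not; it leaves the method open. The caution applies only if actual use is chosen as the splitting variable.
- **A statistical analysis plan may add safeguards.** It may, but it is not at hand, and the Protocol itself fixes the split on use and the two differing event sets.
- **A site-level subgroup answers another question.** Also true. A site protocol is called for only where premedication is used, so the No group may be small, and about 25 sites for 150 neonates (about six each) means the result reflects site practice. It should therefore supplement the actual-use table, not replace it.

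**Conclusion.** The point holds as a design weakness of a secondary safety table. The split is on a post-randomisation variable, chosen with knowledge of the arm and on need, and possibly after the AE that it is meant to classify. Bias in the within-subgroup contrast requires both a difference in use between arms and a link between need and AE risk. Given both, it is roughly 1 to 11 points under the assumed inputs; its sign depends on which arm is sedated more, and it vanishes if either condition fails. The documents establish neither condition, so they support only that a false difference can arise, not that it will.

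Since the subgroup half-widths exceed 20 points, what is at risk is interpretation, not the trial's main safety result. The mismatch in event sets between the synopsis and 12.3.5 is plain on the page and needs no assumption. No view is taken on which sedation practice is appropriate.

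**What to change.** In section 12.3.5 and the synopsis:

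1. Name one AE set for this subgroup in both places.
2. Count sedation/analgesia as Yes only if it was started before laryngoscope insertion. Drug times are recorded (6.2.3.2), and insertion is the defined start of the procedure (7.1.2, 9). This removes the reverse-order problem but not the selection by need.
3. Report use by arm, and label the actual-use table descriptive and non-randomised, with no treatment-effect interpretation.
4. For any between-arm subgroup comparison, classify neonates by whether their site's pre-enrolment protocol foresees pharmacological premedication, with sites that have no protocol counted as No. This precedes randomisation, and site is already a stratification factor.

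Apply items 2 to 4 to any exploratory MV analysis under 12.3.4 that uses sedation.

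**Cost.** Wording in the Protocol and the statistical analysis plan. No new data are needed, because the site protocols go to the sponsor anyway, and clinical practice does not change. The downside is that the site-level subgroup is coarser, reflects site practice rather than individual use, and may have few neonates in its No group.
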